EFFECTIVENESS OF INDIVIDUALIZED
DIETARY COUNSELING AND
NUTRITIONAL MONITORING IN
REDUCING CANCER-ASSOCIATED
CACHEXIA AMONG FEMALE BREAST
CANCER PATIENTS

Submitted by

[name] and [name]

07 February 2024

Effectiveness of Individualized Dietary Counseling and Nutritional Monitoring in Reducing Cancer-Associated Cachexia among Female Breast Cancer Patients

INTRODUCTION

Background of the Study

Cancer-associated cachexia (CACS) is a multifactorial syndrome marked by involuntary weight loss, muscle wasting, systemic inflammation, and metabolic abnormalities. Among patients with advanced-stage breast cancer, CACS significantly impacts quality of life, treatment tolerance, and survival. In low- and middle-income countries like Pakistan, cachexia often remains underdiagnosed and poorly managed due to limited supportive care resources. This study aims to assess the effectiveness of personalized dietary counseling and regular nutritional monitoring in reducing cachexia severity using the validated Mini-CASCO tool.

Objectives of the Study

Primary Objective:

- To evaluate whether individualized dietary counseling combined with monthly nutritional monitoring reduces cachexia severity over six months in female patients with advanced breast cancer.

Secondary Objectives:

- To assess changes in body composition, appetite, physical performance, inflammatory markers, and quality of life.
- To determine the adherence and feasibility of implementing nutrition-sensitive supportive care in an oncology setting.

METHODOLOGY

Study Design

This is a two-arm; parallel-group, randomized controlled trial (RCT) conducted over a six-month intervention period at Fauji Foundation Hospital, Rawalpindi, Pakistan. Participants will be randomly assigned (1:1) to receive either standard oncological care alone (control group) or standard care plus tailored nutritional counseling and monthly monitoring (intervention group). Randomization will be block-stratified with allocation concealment using opaque, sealed envelopes.

Patient Selection and Enrollment

Inclusion Criteria:

- Female patients aged 20–60 years.
- Histologically confirmed advanced-stage breast cancer.
- $\geq 5\%$ unintentional weight loss in the previous 6 months.
- Hemoglobin < 12 g/dL or energy intake < 1500 kcal/day.

Exclusion Criteria:

- Concurrent non-cancer-related malnutrition.
- Pregnancy or lactation.
- GI/endocrine disorders affecting nutrition.

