Statistical Analysis Plan (SAP)

Effectiveness of Individualized Dietary
Counseling and Nutritional
Monitoring in Reducing Cancer-
Associated Cachexia among Female
Breast Cancer Patients: A
Randomized Controlled Trial

07 February, 2024

Introduction

This SAP outlines the pre-specified statistical methodology used to evaluate the effectiveness of individualized dietary counseling combined with regular nutritional monitoring in reducing cancer-associated cachexia among female breast cancer patients. The protocol adheres to the CONSORT guidelines.

Objectives

Primary Objective:

To assess the effect of individualized dietary counseling and regular nutritional monitoring on cachexia severity using the Mini-CASCO tool after six months.

Secondary Objectives:

To evaluate changes in:

- Body composition
- Inflammatory and metabolic markers
- Physical performance
- Appetite levels
- Quality of life (QoL)

Study Design

- **Design:** Prospective, parallel-arm, randomized controlled trial
- **Randomization:** 1:1 ratio with block-stratified randomization (block size = 4)
- **Blinding:** Outcome assessors and statisticians were blinded

Sample Size Determination

Using G*Power for repeated-measures ANCOVA:

- Effect size (Cohen's d): 0.5
- Power: 80%
- Alpha: 0.05
- Estimated N: 64 per group (total 128)
- Final enrollment: 134 randomized; 130 completed (65 per group)

Handling of Missing Data

- Missing data (<5%) addressed via Multiple Imputation (Chained Equations, 10 iterations)
Assumed Missing At Random (MAR)
Sensitivity analyses compared results with and without imputation

Effect Size Estimations

- Cohen's d: within-group effect size
- Partial eta squared (η^2): between-group comparisons
- Interpretation thresholds:
 - $d \geq 0.8$ = large
 - $\eta^2 \geq 0.14$ = large

Software

- Statistical analyses were performed using IBM SPSS Statistics v25.0
- Graphs and tables created using Excel and SPSS

Validation and Sensitivity Analyses

Key assumptions for ANCOVA validated:

- Normality via Shapiro-Wilk test
- Homogeneity of variance via Levene's test
- Sphericity via Mauchly's test
- Sensitivity analysis excluding imputed data showed similar trends

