Appendix A: List of Variables

Outcome Measures Table

| Outcome | Type | Statistical Test | Covariates | Assumption Checks |
|---|-----------|----------------------------------|-----------------|--|
| Change in total Mini-CASCO score | Primary | Repeated-measures ANCOVA | Baseline score | Normality, sphericity (Mauchly's test) |
| Domain-specific Mini-CASCO changes | Secondary | Repeated-measures ANCOVA | Baseline scores | Same as above |
| Within-group differences | Secondary | Paired t-tests | | Normality |
| Between-group effect size | Secondary | Partial eta squared (η^2) | | |
| Compliance/adherence | Secondary | Frequency, percentage | | |

List of Variables Table

| Variable | Type | Tool/Scale |
|------------------------------|-----------------|--|
| Weight | Continuous | Digital scale |
| Lean body mass | Continuous | Bioelectrical impedance analysis |
| CRP, Albumin, Hb, TLC | Continuous | Blood test |
| ECOG performance | Ordinal | ECOG Scale |
| Appetite | Ordinal | Simplified Nutritional Appetite Questionnaire (SNAQ) |
| QoL | Continuous | EORTC QLQ-C30 (Urdu version) |
| Total Mini-CASCO | Composite score | 0–100 scale |

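### The planned effect measures give neither the direction nor the size, in points, of the between-arm difference in Mini-CASCO

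*SAP*

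**What the plan says.** The SAP's Effect Size Estimations section names two measures and gives each one task: "Cohen's d: within-group effect size" and "Partial eta squared (η^2): between-group comparisons". It labels d as large from 0.8 and eta squared as large from 0.14. The outcome table in Appendix A repeats the split. Partial eta squared is the between-group effect size, and within-group differences are tested by paired t-tests; both rows are secondary.

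The primary row reads "Change in total Mini-CASCO score | Primary | Repeated-measures ANCOVA | Baseline score". The variables table describes total Mini-CASCO as a composite on a 0–100 scale. The SAP's primary objective is the effect on cachexia severity after six months.

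The other Cohen's d in the documents is the planning value in Sample Size Determination, "Effect size (Cohen's d): 0.5", which leads to "Estimated N: 64 per group (total 128").

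Neither document specifies an adjusted between-arm difference in points, a confidence interval for it, a between-group d, or a six-month contrast from the repeated-measures model.

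**The concern.** The trial asks whether counselling and monitoring lower cachexia severity compared with standard care. The answer is a difference between arms, with a direction and a size that a clinician can weigh. The SAP goes further than leaving this open: it chooses an effect measure for each purpose, and neither choice supplies the answer.

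Partial eta squared is a share of variance. It is the same whichever arm does better, it cannot be turned back into Mini-CASCO points without further information, and it depends on what else is in the model. Within-group d has a sign, but it describes change over time in one arm. Any course of disease, concurrent oncology treatment or regression to the mean that both arms share goes into it together with any treatment effect.

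The trial could therefore report a significant primary test with effect sizes from which a reader cannot recover the effect. A reader who sets the reported d beside the planned 0.5 would be comparing two different quantities.

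**Working it through.** **Inputs from the SAP.** d = 0.5, power 80%, alpha 0.05, 64 per group; 65 completers per group; 1:1 allocation; thresholds of 0.8 (d) and 0.14 (eta squared); baseline score as covariate. **Assumptions.** The documents give no SD, no correlation and no sidedness. I take alpha as two-sided, show correlations of 0.3, 0.5 and 0.7, and work in SD units.

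**1. Which d gives 64 per group?**

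- Two-sample t-test, between-group d = 0.5: exact n = 63.77 per arm, so 64. Power is 0.801 at 64 and 0.795 at 63. The SAP's figure is reproduced.
- Paired comparison, within-group d = 0.5: exact n = 33.37, so 34 patients. Not reproduced.
- One-sided two-sample test: about 50–51 per arm. Not reproduced.
- Repeated-measures between-factor test (f = d/2 = 0.25, assumed between-visit correlation 0.5): 98, 86 or 74 in total for 2, 3 or 7 measurements. Not reproduced.

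Of the calculations tried, only the two-sided between-group reading returns 64. The d used for planning is not the d that will be reported.

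**2. What partial eta squared shows under the planned model.** For two equal arms with a baseline covariate of correlation r,

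eta² = d² / [d² + 4(1 − r²)].

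For d = +0.5 or −0.5, d² = 0.25:

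| r | 4(1 − r²) | eta² | \|d\| at which eta² = 0.14 |
|---|---|---|---|
| 0.3 | 3.64 | 0.25/3.89 = 0.064 | 0.77 |
| 0.5 | 3.00 | 0.25/3.25 = 0.077 | 0.70 |
| 0.7 | 2.04 | 0.25/2.29 = 0.109 | 0.58 |

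The last column is 2·√(0.14/0.86)·√(1 − r²) = 0.807·√(1 − r²).

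The sign drops out because d is squared. One and the same difference of 0.5 SD gives values from 0.064 to 0.109, depending only on how strongly baseline predicts outcome. At all three correlations the planned effect stays below the SAP's threshold for large.

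A simulation of baseline-adjusted ANCOVA agrees (65 per arm, r = 0.5, 4,000 trials per scenario). When one arm improved by 1.0 SD and the other by 0.5 SD, the adjusted difference was −0.50 SD and mean eta² 0.084. With the arms swapped, the difference was +0.50 SD and mean eta² 0.085. These means lie slightly above 0.077 because sample eta² is biased upward.

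**3. What within-group d shows.** With equal SDs before and after, the SD of change is √[2(1 − r)] baseline SDs, where r is the pre-post correlation. Taking that as the denominator (the SAP defines none),

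within-group d = (shared change + treatment effect) / √[2(1 − r)].

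The numerator cannot be separated within one arm. With no treatment effect, the shared change that would give d = 0.8 is 0.8·√[2(1 − r)] = 0.95, 0.80 or 0.62 SD for r = 0.3, 0.5 or 0.7. This shows that d cannot separate the two components. It does not predict that such a change will occur.

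**4. What the replacement would deliver.** The 95% CI half-width for the adjusted difference with 65 per arm is about 1.979·√(2/65)·√(1 − r²) = 0.33, 0.30 or 0.25 SD for r = 0.3, 0.5 or 0.7. It cannot be given in Mini-CASCO points, because the documents state no SD.

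**The case against.** The strongest reply is that the plan already contains a proper randomized comparison. The primary analysis is a between-arm ANCOVA adjusted for baseline, within-group results are secondary, and no rule makes a d of 0.8 a criterion for success. Listing standardized measures does not exclude adjusted means, which the same model can produce. All of this stands. It limits the fault to the effect measure and leaves the test untouched.

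It does not remove the fault. The SAP has a section for effect sizes and an outcome row for the between-group effect, and both name partial eta squared. A difference that may or may not be taken from the output later is not pre-specified.

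Three stronger readings are tempting, and the documents do not support them:

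- *That the trial will claim success from within-group change.* A large within-group d cannot make the primary test significant. When both arms were simulated with the same 1.0 SD improvement, the intervention arm reached |d| ≥ 0.8 in 92% of trials, but the ANCOVA was significant in only 5.1%.
- *That a large within-group d is to be expected without any treatment effect.* Entry requires recent weight loss together with "Hemoglobin < 12 g/dL or energy intake < 1500 kcal/day", so some regression to the mean is plausible. But the documents do not list the Mini-CASCO items and give no retest data, and deterioration in advanced disease could offset it. The shared 1.0 SD improvement is an assumption.
- *That a negative difference means benefit.* The SAP gives the range of the score but not which end is worse.

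**Conclusion.** The concern holds as a fault in the planned effect measure. Partial eta squared, the only between-group measure named, gives no direction and no points. Within-group d cannot separate treatment from change common to both arms, and it is not the quantity behind the planning value of 0.5.

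The lack of sign and units follows from the definition and rests on no assumption. The spread from 0.064 to 0.109 rests on the assumed correlations and on a single adjusted outcome. The match of 64 per group to a between-group d rests on a two-sided alpha. The validity of the primary test is not in question, and the sample size need not change on this account. The change is worth making because it decides what the trial can say about the size of its effect, at very little cost.

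**What to change.** - Define the primary effect estimate as the baseline-adjusted between-arm difference in total Mini-CASCO at six months, in points, with a 95% CI. State which sign favours the intervention, according to the instrument's scoring.
- Report beside it a signed between-group standardized difference with its denominator defined, so that it can be read against the planned 0.5.
- Keep partial eta squared as a supplementary figure.
- Label within-group d and the paired t-tests as descriptive, and state that they are not evidence of a treatment effect.

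**Cost.** The change needs SAP wording and output from the model already planned. It needs no further patients or visits. The reported effect may look smaller than a within-group d. The SAP already gives completion figures ("Final enrollment: 134 randomized; 130 completed (65 per group") and says that the sensitivity analysis showed similar trends. The change should therefore be declared as an amendment with its date and not presented as part of the plan from the start.

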Appendix A: List of Variables

Outcome Measures Table

| Outcome | Type | Statistical Test | Covariates | Assumption Checks |
|---|-----------|----------------------------------|-----------------|--|
| Change in total Mini-CASCO score | Primary | Repeated-measures ANCOVA | Baseline score | Normality, sphericity (Mauchly's test) |
| Domain-specific Mini-CASCO changes | Secondary | Repeated-measures ANCOVA | Baseline scores | Same as above |
| Within-group differences | Secondary | Paired t-tests | | Normality |
| Between-group effect size | Secondary | Partial eta squared (η^2) | | |
| Compliance/adherence | Secondary | Frequency, percentage | | |

List of Variables Table

| Variable | Type | Tool/Scale |
|------------------------------|-----------------|--|
| Weight | Continuous | Digital scale |
| Lean body mass | Continuous | Bioelectrical impedance analysis |
| CRP, Albumin, Hb, TLC | Continuous | Blood test |
| ECOG performance | Ordinal | ECOG Scale |
| Appetite | Ordinal | Simplified Nutritional Appetite Questionnaire (SNAQ) |
| QoL | Continuous | EORTC QLQ-C30 (Urdu version) |
| Total Mini-CASCO | Composite score | 0–100 scale |

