- Enrollment involved screening for eligibility, obtaining informed consent, and randomization using sealed, opaque envelopes.

Baseline data were collected before group assignment.

Eligible patients will undergo informed consent. Those consenting will be randomized using a block randomization method. Baseline data will be collected prior to group assignment.

Intervention

Intervention Group:

- Individualized dietary counseling based on baseline nutritional status
- Monthly monitoring (every 15–21 days) of weight, intake, and biochemical parameters
- Light physical activity guidance and psychosocial support
- Dietary goals: 25–30 kcal/kg/day and 1.2–1.5 g/kg/day protein
- Compliance tracked through food intake records and goal adherence checklists

Control Group:

Standard oncological care without structured nutritional intervention

Ethical Considerations

This study will be approved by the Ethical Review Board of Fauji Foundation Hospital, Rawalpindi. All participants will provide written informed consent prior to enrollment. The study adheres to the ethical principles outlined in the Declaration of Helsinki. Confidentiality will be ensured through unique patient identifiers and restricted data access.

Protocol Amendments

No protocol amendments have been made to date. Any future amendments will be reviewed and approved by the Ethical Review Board and documented accordingly in the PRS system.

REFERENCES

4. World Health Organization. *Global Breast Cancer Initiative Implementation Framework: Saving Lives, Improving Quality of Care.* Geneva: World Health Organization; 2021. Available from: <https://www.who.int/publications/i/item/9789240022616>

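### The primary model leaves out the strata that randomisation is said to have used, and it names neither its deciding term nor the Mini-CASCO visits

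*SAP*

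**What the plan says.** **Primary model.** The Outcome Measures Table in SAP Appendix A gives "Change in total Mini-CASCO score | Primary | Repeated-measures ANCOVA | Baseline score", followed by checks of normality and of sphericity by Mauchly's test. No model term and no list of visits is given there or elsewhere.

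**Randomisation.** SAP, Study Design: "1:1 ratio with block-stratified randomization (block size = 4". Protocol, Study Design: "Randomization will be block-stratified with allocation concealment using opaque, sealed envelopes". Protocol, Patient Selection and Enrollment, says only that patients are "randomized using a block randomization method". No stratification factor is named anywhere.

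**Time frame.** The SAP's primary objective is an effect "on cachexia severity using the Mini-CASCO tool after six months". The Protocol's primary objective speaks of a reduction in severity over six months.

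**Visits.** The Protocol lists repeated monitoring for the intervention group only. It covers weight, intake and biochemistry, not Mini-CASCO.

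**Sample size and status.** SAP, Sample Size Determination: "Using G*Power for repeated-measures ANCOVA", with Cohen's d of 0.5, 80% power and alpha 0.05, leading to "Estimated N: 64 per group (total 128". It then reports "Final enrollment: 134 randomized; 130 completed (65 per group". The Validation and Sensitivity Analyses section already describes a sensitivity result.

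**Between-group summary.** The only one named is partial eta squared.

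**The concern.** There are two separate gaps.

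*Strata.* Stratified randomisation balances the arms on the strata, so chance imbalance on those factors no longer adds to the variability of the treatment difference. A model without the strata still counts their variation as noise. Its standard error is then larger than the true sampling error. If no strata were used, the model is fine and the description of the randomisation is wrong.

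*Deciding term.* A repeated-measures ANCOVA can yield a group effect averaged over visits, a group-by-time effect, and a month-6 contrast. With several visits these are different questions, and one can be significant while another is not. A plan that names none of them leaves the primary result undefined. Partial eta squared does not repair this: its source term is not named, and it does not show the difference on the 0–100 scale.

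**Working it through.** **1. The plan's own sample size.** For a two-sided two-sample t-test with d = 0.5, the noncentrality is λ = (n/2)d². At n = 64, λ = 32 × 0.25 = 8 and F(1,126) gives 80.1% power. At n = 63, λ = 7.875 and power is 79.5%. A one-covariate ANCOVA with f = 0.25 and N = 128 has λ = 0.0625 × 128 = 8 on F(1,125), again 80.1%. So 64 per group is the size for a single two-arm comparison.

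Under the label given, a repeated-measures between-group test has λ = 0.0625·N·m/(1+(m−1)ρ). With m = 2 to 7 measurements and ρ = 0.3 to 0.7 (assumed), it needs 54–110 patients in total, not 128. The sample-size section therefore gives no number of visits, correlation or tested term from which the deciding test could be inferred.

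**2. Strata.** Assumption: the strata are balanced between arms and explain a fraction R² of the variance left after baseline.

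- Ratio of reported to true standard error: 1/√(1−R²)
- Type I error: 2[1 − Φ(1.96/√(1−R²))]

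| R² | SE overstated | Type I error, formula | Type I error, simulated | Power gained by adding strata, d on baseline-adjusted SD | Same, d on raw SD |
|---|---|---|---|---|---|
| 5% | 2.6% | 4.4% | 4.4–4.5% | 1.3–1.4 points | 0.7–0.9 |
| 10% | 5.4% | 3.9% | 4.0–4.2% | 2.6–2.8 | 1.7–1.8 |
| 20% | 11.8% | 2.8% | 2.8–2.9% | 5.2–5.6 | 2.9–3.0 |

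The simulation used permuted blocks of 4 within 2 or 4 strata, N = 130, baseline correlation 0.5 and 12,000 replicates per cell. Both scales are shown because the SAP does not say which SD its d of 0.5 refers to. With strata in the model, type I error was 4.9–5.1%. Mean estimates were the same with and without strata. Non-prognostic strata cost at most 0.1 point of power.

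A hand check at R² = 10%, d on the adjusted SD: δ = 0.5√0.75 = 0.433. The reported SE without strata is √(0.75 × 2/65) = 0.1519. The true SE is 0.1519 × √0.9 = 0.1441.
- Without strata: power = Φ((0.433 − 1.979 × 0.1519)/0.1441) = Φ(0.919) = 82.1%.
- With strata: power = Φ(0.433/0.1441 − 1.979) = Φ(1.026) = 84.7%.
- Gain: 2.7 points from unrounded values, in line with the simulation.

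**3. Deciding term, baseline and month 6 only.** Let b be baseline and y the month-6 score. Once b is a covariate, regressing y, y − b or (y + b)/2 on arm changes the arm coefficient and its standard error only by a common factor (1, 1 and ½). The t-statistics are identical, so the term issue disappears. Sphericity also has no content with two levels.

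**4. Deciding term, more visits.** Assumptions: two post-baseline visits, equal correlation ρ = 0.3–0.7, 65 per arm.

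- Month-6 contrast: residual variance 1 − ρ².
- Group effect averaged over post-baseline visits: residual variance (1+ρ)/2 − ρ².
- Group-by-time, baseline as covariate only: λ = 32.5·Σ(d_k − mean d)²/(1−ρ), F(1,127).
- Group-by-time, baseline also a level of the repeated factor: joint test, λ = 32.5·d′S⁻¹d with S = (1−ρ)I + (ρ−ρ²)J (J the matrix of ones), F(2,126).

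Power in %, effect on the raw SD / on the baseline-adjusted SD:

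| Effect at first visit → month 6 | Month-6 contrast | Averaged group effect | Group-by-time, baseline covariate only | Group-by-time, baseline also a level |
|---|---|---|---|---|
| 0.25 → 0.5 | 84–98 / 81 | 81–94 / 71–77 | 22–45 / 21–26 | 79–95 / 72–75 |
| 0.5 → 0.5 | 84–98 / 81 | 97–99.7 / 92–95 | 5 / 5 | 93–99 / 86–91 |
| 0 → 0.5 | 84–98 / 81 | 47–65 / 39–44 | 67–96 / 63–74 | 78–98 / 74–80 |
| 0.5 → 0.25 | 32–51 / 29 | 81–94 / 71–77 | 22–45 / 21–26 | 79–95 / 72–75 |

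No term is best throughout. The ranking depends on the effect trajectory, and the group-by-time figures also depend on how baseline is coded. The documents state neither.

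**The case against.** The strongest reply is that the trial may have only two Mini-CASCO measurements. The outcome is a change, within-group differences are tested by paired t-tests, and baseline and six months are the only times the text implies. Step 3 shows that the choice of term then has no effect. This stands as a possibility. Against it, the SAP plans Mauchly's test in two places, which is meaningful only with three or more levels. Either way something needs correcting: the term must be named, or the sphericity check is empty.

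It is also fair to say that the Protocol's time frame could support an averaged or trajectory question, so the documents do not settle on month 6. The month-6 difference is recommended because it matches the SAP objective, not because it is always the most powerful. The most extreme contrast in step 4 (5% against 97–99.7%) arises only if baseline is not a level of the repeated factor.

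On strata, the enrolment text mentions blocks alone, so the word stratified may simply be loose. The R² values are assumptions.

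Three stronger readings are tempting and not supported:
- A reader might infer that omitting strata biases the result or inflates false positives. The effect runs the other way: the test is conservative and the estimate unbiased.
- A reader might infer that the sample size is wrong. It reproduces as a single two-arm comparison; only its label does not fit.
- A reader might infer that a favourable term was chosen after seeing results. The documents leave room for that but do not show it.

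**Conclusion.** The point holds, in two parts of limited size.

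The description of randomisation and the primary model do not match. If strata were used and explain 5–20% of residual variance, the analysis gives up about 1–6 points of power and runs at about 4.4–2.8% type I error instead of 5%. If they are not prognostic, nothing material is lost. If there were none, the fault is in the wording.

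The deciding term and the visits are unspecified. This has no consequence with baseline and month 6 only. With three or more measurements, which the planned sphericity test suggests, it leaves the primary question open among tests whose power differs widely. The size cannot be fixed further, because the number of visits, the correlation, the effect trajectory and the coding of baseline are not in the documents. It should be corrected. It does not show that the trial's result is invalid.

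**What to change.** 1. Name the randomisation strata and add them to the primary model. If none were used, delete the word stratified from the SAP and from the Protocol's Study Design section; the strata covariates then fall away.
2. State the Mini-CASCO visit times in both arms, and say whether baseline is a covariate only or also a level of the repeated factor. If there are only two measurements, drop the sphericity check.
3. Reconcile the two time frames in the SAP and Protocol objectives.
4. Disclose which model term was used as the primary test.
5. Report the between-arm difference in total Mini-CASCO at month 6, adjusted for baseline and any strata, with its 95% CI, beside partial eta squared. An ANCOVA at month 6 is enough. If both arms share intermediate visits, the month-6 contrast of a mixed model with the same covariates also serves.

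Timing matters, because the SAP already reports completion and a sensitivity result. If unblinded results have not been seen, make this a dated amendment. If they have, keep the original model and report the new one beside it as a labelled additional analysis.

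Cost: no extra patients or visits. With 130 completers and three parameters (intercept, arm, baseline) there are 127 residual degrees of freedom. Two to four strata use 1 to 3 of them. The rest is a little more analysis and reporting.
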